2.7 Special notes on response assessment

When nodal disease is included in the sum of target lesions and the nodes decrease to 'normal' size (<10 mm), they may still have a measurement reported on scans. This measurement should be recorded even though the nodes are normal in order not to overstate progression should it be based on increase in size of the nodes. As noted earlier, this means that patients with CR may not have a total sum of 'zero' on the case report form (CRF).

In trials where confirmation of response is required, repeated 'NE' time point assessments may complicate best response determination. The analysis plan for the trial must address how missing data/assessments will be addressed in determination of response and progression. For example, in most trials it is reasonable to consider a patient with time point responses of PR-NE-PR as a confirmed response.

Patients with a global deterioration of health status requiring discontinuation of treatment without objective evidence of disease progression at that time should be reported as 'symptomatic deterioration'. Every effort should be made to document objective progression even after discontinuation of treatment. Symptomatic deterioration is not a descriptor of an objective response: it is a reason for stopping study therapy. The objective response status of such patients is to be determined by evaluation of target and non-target disease as shown in Tables 1-3 below.

Conditions that define 'early progression, early death and inevaluability' are study specific and should be clearly described in each protocol (depending on treatment duration, treatment periodicity).

In some circumstances it may be difficult to distinguish residual disease from normal tissue. When the evaluation of complete response depends upon this determination, it is recommended that the residual lesion be investigated (fine needle aspirate/biopsy) before assigning a status of complete response. FDG-PET may be used to upgrade a response to a CR in a manner similar to a biopsy in cases where a residual radiographic abnormality is thought to represent fibrosis or scarring. The use of FDG-PET in this circumstance should be prospectively described in the protocol and supported by disease specific medical literature for the indication. However, it must be acknowledged that both approaches may lead to false positive CR due to limitations of FDG-PET and biopsy resolution/sensitivity.

Table 1 Time point response: patients with target (+/- non-target) disease

| Target lesions | Non-target lesions | New lesions | Overall response |
|----------------|--------------------|-------------|------------------|
| CR | CR | No | CR |
| CR | Non-CR/non-PD | No | PR |

| | | | |
|-------------------|-----------------------------|-----------|----|
| CR | Not evaluated | No | PR |
| PR | Non-PD or not all evaluated | No | PR |
| SD | Non-PD or not all evaluated | No | SD |
| Not all evaluated | Non-PD | No | NE |
| PD | Any | Yes or No | PD |
| Any | PD | Yes or No | PD |
| Any | Any | Yes | PD |

Note: CR=complete response, PR=partial response, SD=stable disease, PD=progressive disease, NE=inevaluable.

Table 2 Time point response: patients with non-target disease only

| Non-target lesions | New lesions | Overall response |
|--------------------|-------------|------------------|
| CR | No | CR |
| Non-CR/non-PD | No | Non-CR/non-PD |
| Not all evaluated | No | NE |
| Unequivocal PD | Yes or No | PD |
| Any | Yes | PD |

Note: CR=complete response, PD=progressive disease, NE=inevaluable.

'Non-CR/non-PD' is preferred over 'stable disease' for non-target disease since SD is increasingly used as endpoint for assessment of efficacy in some trials so to assign this category when no lesions can be measured is not advised.

For equivocal findings of progression (e.g. very small and uncertain new lesions; cystic changes or necrosis in existing lesions), treatment may continue until the next scheduled assessment. If at the next scheduled assessment, progression is confirmed, the date of progression should be the earlier date when progression was suspected.

Table 3 Best overall response when confirmation of CR and PR required

| Overall response First time point | Overall response Subsequent time point | BEST overall response |
|-----------------------------------|--|---|
| CR | CR | CR |
| CR | PR | SD, PD, or PR ^a |
| CR | SD | SD provided minimum criteria for SD duration met, otherwise, PD |
| CR | PD | SD provided minimum criteria for SD duration met, otherwise, PD |
| CR | NE | SD provided minimum criteria for SD duration met, otherwise NE |
| PR | CR | PR |
| PR | PR | PR |
| PR | SD | SD |
| PR | PD | SD provided minimum criteria for SD duration |

| Overall response First time point | Overall response Subsequent time point | BEST overall response |
|--------------------------------------|---|---|
| | | met, otherwise, PD |
| PR | NE | SD provided minimum criteria for SD duration met, otherwise NE |
| NE | NE | NE |

Note: CR=complete response, PR=partial response, SD=stable disease, PD=progressive disease, NE=inevaluable.

a. If a CR is truly met at first time point, then any disease seen at a subsequent time point, even disease meeting PR criteria relative to baseline, makes the disease PD at that point (since disease must have reappeared after CR). Best response would depend on whether minimum duration for SD was met. However, sometimes 'CR' may be claimed when subsequent scans suggest small lesions were likely still present and in fact the patient had PR, not CR at the first time point. Under these circumstances, the original CR should be changed to PR and the best response is PR.

2.8 Confirmatory measurement/duration of response

Confirmation

In non-randomized trials where response is the primary endpoint, confirmation of PR and CR is required to ensure responses identified are not the result of measurement error. In randomized trials (phase II or III) or studies where stable disease or progression are the primary endpoints, confirmation of response is not required since it will not add value to the interpretation of trial results. In the case of SD, measurements must have met the SD criteria at least once after study entry at a minimum interval (in general not less than 6–8 weeks) that is defined in the study protocol.

Duration of overall response

The duration of overall response is measured from the time measurement criteria are first met for CR/PR (whichever is first recorded) until the first date that recurrent or progressive disease is objectively documented (taking as reference for progressive disease the smallest measurements recorded on study). The duration of overall CR is measured from the time measurement criteria are first met for CR until the first date that recurrent disease is objectively documented.

Duration of stable disease

Stable disease is measured from the start of the treatment (in randomized trials, from date of randomization) until the criteria for progression are met, taking as reference the smallest sum on study (if the baseline sum is the smallest, this is the reference for calculation of PD). The clinical relevance of the duration of stable disease varies in different studies and diseases. If the proportion of patients achieving stable disease for a minimum period of time is an endpoint of importance in a particular trial, the protocol should specify the minimal time interval required between two measurements for determination of stable disease.

Note: The duration of response and stable disease as well as the progression-free survival are influenced by the frequency of follow-up after baseline evaluation. It is not in the scope of this guideline to define a standard follow-up frequency. The

frequency should take into account many parameters including disease types and stages, treatment periodicity and standard practice. However, these limitations of the precision of the measured endpoint should be taken into account if comparisons between trials are to be made.

2.9 Progression-free survival/proportion progression-free

Phase III trials in advanced cancers are increasingly designed to evaluate progression-free survival or time to progression as the primary outcome of interest. Assessment of progression is relatively straightforward if the protocol requires all patients to have measurable disease. Increasingly, trials allow entry of both patients with measurable disease as well as those with non-measurable disease only. In this circumstance, care must be taken to explicitly describe the findings which would qualify for progressive disease for those patients without measurable lesions. Because the date of progression is subject to ascertainment bias, timing of investigations in study arms should be the same.

Comparison of irRECIST With RECIST v1.1

Source: Hodi FS, Ballinger M, Lyons B, et al. Immune-Modified Response Evaluation Criteria In Solid Tumors (irRECIST): Refining Guidelines to Assess the Clinical Benefit of Cancer Immunotherapy. *J Clin Oncol*. 2018 Mar 20;36(9):850-858.

Full text link: http://ascopubs.org/doi/abs/10.1200/JCO.2017.75.1644?url_ver=Z39.88-2003&rft_id=ori:rid:crossref.org&rft_dat=cr_pub%3dpubmed

Briefly, immune-modified Response Evaluation Criteria in Solid Tumors (irRECIST) allows for collection of additional scans and for BOR to occur after radiologic PD assessment(s) in patients continuing treatment (see Table 4 below). New lesions are added to the total tumor burden along with the sum of the target lesions when measurable; when not measurable, they are not factored into the PD assessment. In addition, progression in non-target lesions does not define PD. For analysis of irRECIST-defined PFS (impFS), irRECIST PD or death is considered an event; however, an irRECIST PD is not considered an impFS event if the time point response at the subsequent scan (≥ 4 weeks later) is irRECIST SD/PR/CR. An irRECIST PD followed by no additional assessments is considered an impFS event.

Table 4 Comparison of RECIST 1.1 With irRECIST

| Criterion | RECIST v1.1 | irRC | irRECIST* |
|--------------------|---|---|---|
| Tumor burden | Unidimensional Up to 5 target lesions/2 per organ | Bidimensional per WHO Up to 10 target lesions/ 5 per organ | Unidimensional, with other target lesion criteria (number, measurability) per RECIST v1.1 |
| New lesions | Always represent PD | New lesions do not categorically define PD Measurable new lesions incorporated into the total tumor burden Non-measurable new lesions preclude CR | |
| Non-target lesions | Can contribute to defining CR or PD (unequivocal progression) | Non-target progression does not define PD Can only contribute to defining CR (complete disappearance required) | |
| PD | $\geq 20\%$ increase in the SLD (RECIST) and ≥ 5 mm increase compared with nadir, unequivocal progression in nontarget lesions, and/or appearance of new lesions | Determined only on the basis of measurable disease | |
| | | Negated by subsequent non-PD assessment ≥ 4 weeks from the date first documented (lack of confirmation) | |
| | | $\geq 25\%$ increase in the SLD compared with baseline/ nadir | $\geq 20\%$ increase in SLD (RECIST) compared with baseline/ nadir |
| | Confirmation of PD not required | Best response may occur before confirmed PD | Best response may occur after any number of PD assessments |

Note: CR=complete response, irRECIST=immune-modified RECIST, irRC=immune-related response criteria, PD=progressive disease, RECIST=Response Evaluation Criteria in Solid Tumors, SLD=sum of longest diameters.

*irRECIST follows RECIST v1.1 conventions unless otherwise stated.

IrRECIST is derived from RECIST v1.1 conventions and immune-related response criteria (irRC)¹. When not otherwise specified, RECIST v1.1 conventions will apply.

Table 5 irRECIST and RECIST v1.1: Summary of Changes

| | RECIST v1.1 | irRECIST |
|----------------------------|--|--|
| New lesions after baseline | Define progression. | New measurable lesions are added into the total tumor burden and followed. |
| Non-target lesions | May contribute to the designation of overall progression. | Contribute only in the assessment of a CR. |
| Radiographic progression | First instance of $\geq 20\%$ and $\geq 5\text{mm}$ increase in the sum of diameters or unequivocal progression in non-target disease. | Determined only on the basis of measurable disease. |

Note: CR=complete response, irRECIST=immune-modified RECIST, RECIST=Response Evaluation Criteria in Solid Tumors.

Target Lesions

When more than one measurable lesion is present at baseline, all lesions up to a maximum of 5 lesions total (and a maximum of 2 lesions per organ) representative of all involved organs should be identified as target lesions and will be recorded and measured at baseline.

Non-Target Lesions

After baseline, changes in non-target lesions will contribute only in the assessment of CR (i.e., a CR is attained only with the complete disappearance of all tumor lesions, including non-target lesions) and will not be used to assess progressive disease.

New Lesions

During the study, all new lesions identified and recorded after baseline must be assessed at all tumor assessment timepoints. New lesions will also be evaluated for measurability with use of the same criteria applied to prospective target lesions at baseline per RECIST, (e.g., non-lymph node lesions must be $\geq 10\text{ mm}$; see note for new lymph node lesions below). Up to a maximum of 5 new lesions total (and a maximum of 2 lesions per organ), all with measurements at all timepoints, can be included in the tumor response evaluation. New lesion types that would not qualify as target lesions per RECIST cannot be included in the tumor response evaluation, but can be used for CR exclusion.

New lesions that are not measurable at first appearance but meet measurability criteria at a subsequent timepoint will be measured from that point on and contribute to the sum of longest diameters (SLD), if the maximum number of 5 measurable new lesions being followed has not been reached.

Calculation of Sum of the Diameters

¹ Wolchok et al. Clin Can Res 2009;15:7412–20; Nishino et al. J Immunother Can 2014;2:17; Nishino et al. Clin Can Res 2013;19:3936–43.

A sum of the diameters (longest for non-nodal lesions, short axis for nodal lesions) for all target lesions will be calculated as a measure of tumor burden.

The sum of the diameters is calculated at baseline and at each tumor assessment for the purpose of classification of tumor responses.

Sum of the Diameters at Baseline: The sum of the diameters for all target lesions identified at baseline prior to treatment on Day 1.

Sum of the Diameters at Tumor Assessment: For every on-study tumor assessment collected per protocol or as clinically indicated the sum of the diameters at tumor assessment will be calculated using tumor imaging scans. All target lesions selected at baseline and up to 5 new measurable lesions (with a maximum of 2 new lesions per organ) that have emerged after baseline will contribute to the sum of the diameters at tumor assessment. Hence, each net percentage change in tumor burden per assessment with use of modified RECIST accounts for the size and growth kinetics of both old and new lesions as they appear.

Note: In the case of new lymph nodes, RECIST v1.1 criteria for measurability (equivalent to baseline target lesion selection) will be followed. That is, if at first appearance the short axis of a new lymph node lesion ≥ 15 mm, it will be considered a measurable new lesion and will be tracked and included in the SLD. Thereafter, the lymph node lesion will be measured at subsequent timepoints and measurements will be included in the SLD, even if the short axis diameter decreases to <15 mm (or even <10 mm). However, if it subsequently decreases to < 10 mm, and all other lesions are no longer detectable (or have also decreased to a short axis diameter of < 10 mm if lymph nodes), then a response assessment of CR may be assigned.

If at first appearance the short axis of a new lymph node is ≥ 10 mm and < 15 mm, the lymph node will not be considered measurable but will still be considered a new lesion. It will not be included in the SLD unless it subsequently becomes measurable (short axis diameter ≥ 15 mm).

The appearance of new lymph nodes with diameter < 10 mm should not be considered pathological and not considered a new lesion.

Response Criteria

Timepoint Response

It is assumed that at each protocol-specified timepoint, a response assessment occurs. Table 6 provides a summary of the overall response status calculation at each timepoint for patients who have measurable disease at baseline.

Complete Response (CR): Disappearance of all target and non-target lesions. Lymph nodes that shrink to <10 mm short axis are considered normal.

Partial Response (PR): At least a 30% decrease in the sum of the diameters of all target and all new measurable lesions, taking as reference the baseline sum of diameters, in the absence of CR.

Note: the appearance of new measurable lesions is factored into the overall tumor burden, but does not automatically qualify as progressive disease until the sum of the diameters increases by $\geq 20\%$ when compared with the sum of the diameters at nadir.

Stable Disease (SD): Neither sufficient shrinkage to qualify for PR nor sufficient increase to qualify for PD, taking as reference the smallest sum of the diameters while on study.

Progressive Disease (PD): At least a 20% increase in the sum of diameters of all target and selected new measurable lesions, taking as reference the smallest sum on study (nadir SLD; this includes the baseline sum if that is the smallest on study). In addition to the relative increase of 20%, the sum must also demonstrate an absolute increase of at least 5 mm.

Impact of New Lesions on irRECIST

New lesions alone do not qualify as progressive disease. However, their contribution to total tumor burden is included in the sum of the diameters, which is used to determine the overall modified RECIST tumor response.

Missing Assessments and Not Evaluable Designation

When no imaging/measurement is done at all at a particular timepoint, the patient is considered not evaluable (NE) at that timepoint. If only a subset of lesion measurements are made at an assessment, usually the case is also considered NE at that timepoint, unless a convincing argument can be made that the contribution of the individual missing lesion(s) would not change the assigned timepoint response. This would only happen in the case of PD. For example, if a patient had a baseline sum of 50 mm with 3 measured lesions and at follow-up only 2 lesions were assessed but those gave a sum of 80 mm, the patient will be assigned PD status, regardless of the contribution of the missing lesion.

Table 6 irRECIST Timepoint Response Definitions

| % Change in Sum of the Diameters ^a | Non-Target Lesion Response Assessment | Overall Immune-Modified RECIST Timepoint Response |
|--|--|--|
| -100% from baseline ^b | CR | CR |
| -100% from baseline ^b | Non-CR or not all evaluated | PR |
| ≤ -30% from baseline | Any | PR |
| > -30% to < +20% | Any | SD |
| Not all evaluated | Any | NE |
| ≥ +20% from nadir SLD | Any | PD |

Note: CR=complete response, NE= not evaluable, PD= progressive disease, PR= partial response, RECIST=Response Evaluation Criteria in Solid Tumors, SD= stable disease, SLD= sum of the longest diameter.

- a. Percent change in sum of the diameters (including measurable new lesions when present).
- b. When lymph nodes are included as target lesions, the % change in the sum of the diameters may not be 100% even if CR criteria are met, because a normal lymph node is defined as having a short axis of < 10 mm. Any pathological lymph nodes (whether target or non-target) must have reduction in short axis to <10 mm in order to meet the definition of CR.

Comparison of irRECIST With Conventional RECIST

Source: *Lencioni R, Llovet JM. Modified RECIST (irRECIST) assessment for hepatocellular carcinoma.*

Semin Liver Dis. 2010 Feb;30(1):52-60.

Note the following points regarding modified RECIST (irRECIST):

- irRECIST are recommended by American Association for the Study of Liver Diseases (AASLD) for the assessment of tumor response in HCC.
- Patients can be followed with either contrast-enhanced spiral CT or contrast-enhanced dynamic MRI.
- In contrast-enhanced studies, it is mandatory to obtain a dual-phase imaging of the liver (high-quality arterial-phase imaging obtained on the first run, and high-quality portal venous-phase imaging obtained on the second run).

When assessing tumor response, the longest diameter of the target lesion (either viable or necrotic) is measured in conventional RECIST, whereas only viable target lesions are taken into account in irRECIST (see Table 7 below).

Table 7 Comparison of irRECIST With Conventional RECIST

| Conventional RECIST | irRECIST |
|---|---|
| CR=Disappearance of all target lesions. | CR=Disappearance of any intratumoral arterial enhancement in all target lesions. |
| PR=At least a 30% decrease in the sum of diameters of target lesions, taking as reference the baseline sum of the diameters of target lesions. | PR=At least a 30% decrease in the sum of diameters of viable (enhancement in the arterial phase) target lesions, taking as reference the baseline sum of the diameters of target lesions. |
| SD=Any cases that do not qualify for either PR or PD. | SD=Any cases that do not qualify for either PR or PD. |
| PD=An increase of at least 20% in the sum of the diameters of target lesions, taking as reference the smallest sum of the diameters of target lesions recorded since treatment started. | PD=An increase of at least 20% in the sum of the diameters of viable (enhancing) target lesions, taking as reference the smallest sum of the diameters of viable (enhancing) target lesions recorded since treatment started. |

Note: irRECIST=modified RECIST, CR=complete response, PR=partial response, RECIST=Response Evaluation Criteria in Solid Tumors, SD=stable disease, PD=progressive disease.

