6.6. Treatment Beyond Progression

If the subject has progression as defined in RECIST v1.1, he/she still can continue SHR-1210 alone or combined with apatinib (experimental arm) when he/she can still clinically benefit from and tolerate study treatment, as evaluated by investigators.

6.6.1. Criteria on Post-Progression Continuation of SHR-1210 Alone or Combined With Apatinib in Subjects in Experimental Arm

A part of patients receiving immunotherapy can still clinically benefit following radiological progression. Although the tumor is enlarged, obvious necrosis or degeneration can appear inside the tumor, decreased density inside the tumor foci can be shown on CT, it is generally considered that the patient may benefit under this circumstance. After progression of disease as defined by RECIST v1.1, subjects meeting all of the following criteria may continue with the study treatment. If the disease progression defined by irRECIST is confirmed in a subsequent radiological evaluation, the study treatment will be terminated, unless the investigator considers that the subject can continue to benefit clinically (which has to be further discussed

with and agreed by the sponsor); in the latter case, the subject may continue with the study treatment until the investigator determines that the subject can no more benefit clinically from the study treatment. Subjects who continue the dose following PD will receive periodic visit and efficacy evaluation according to the visit schedule specified in the trial.

- Investigators judge continuation of study treatment meets the best interest for the subject, and the subject does not need to start other antitumor therapy immediately;
- The subject can tolerate study treatment;
- Stable ECOG-PS score (≤ 1);
- No significant clinical symptom/sign of progression of disease, including change in laboratory examination parameters;
- Non-rapid progression of disease and progression not involving major organs/sites (e.g., spinal cord compression);
- The study treatment can be continued upon the review and approval by the medical monitors from the sponsor.

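### irRECIST Table 6 conflicts with the text above it on the 5 mm minimum for progression and on missing lesions, and neither ranks PD over PR

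*Protocol*

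**What the plan says.** All places are in the Protocol.

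- **Appendix 1, irRECIST Response Criteria, Progressive Disease.** The sum of target and selected new measurable lesions must rise at least 20% over the smallest sum on study, and: "In addition to the relative increase of 20%, the sum must also demonstrate an absolute increase of at least 5 mm".
- **Appendix 1, Timepoint Response.** "Table 6 provides a summary of the overall response status calculation at each timepoint", for patients with measurable disease at baseline.
- **Appendix 1, Table 6.** The PD row reads "≥ +20% from nadir SLD | Any | PD". The row for incomplete assessments gives NE whatever the non-target status, with no exception.
- **Appendix 1, Missing Assessments.** An incomplete assessment is usually NE, but PD is the exception. In the example, a baseline sum of 50 mm from three lesions becomes 80 mm from only two of them, and "the patient will be assigned PD status, regardless of the contribution of the missing lesion".
- **Appendix 1, Table 4.** The irRECIST progression cell requires a 20% "increase in SLD (RECIST) compared with baseline/ nadir" and gives no millimetre minimum. The RECIST v1.1 cell beside it prints the 5 mm.
- **Section 7.1.** PFS, ORR, DCR and DoR are defined by RECIST v1.1 or irRECIST.
- **Section 6.6.1.** "If the disease progression defined by irRECIST is confirmed in a subsequent radiological evaluation, the study treatment will be terminated", subject to an exception agreed with the sponsor.

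**The concern.** A table headed as response definitions is what a reader or a programmer is likely to implement. If it disagrees with the prose it summarises, two competent people can classify the same scan differently, and both can point to the protocol. That would move progression dates for irRECIST PFS and the end of response for irRECIST DoR. It also touches the irRECIST progression that Section 6.6.1 uses after RECIST v1.1 progression. The 5 mm minimum is there to stop a small measurement change on a small tumour sum from counting as progression.

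**Working it through.** **Inputs.** Text rule: PD if the current sum C ≥ 1.20 × nadir N and C − N ≥ 5 mm. Table 6 rule: PD if C ≥ 1.20 × N. PR in both: C ≤ 0.70 × baseline B. Entry requires only one measurable lesion of at least 10 mm, or a node of at least 15 mm short axis (Section 4.1, criterion 5). Sums other than 50 and 80 mm are assumed for illustration.

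**1. The plan's own example.** (80 − 50)/50 = +60%, and 80 − 50 = +30 mm. Both text conditions are met, so the stated PD is reproduced. In Table 6 the scan falls in the incomplete row (NE). The measured sum also satisfies the PD row, so the table returns two answers where the text returns one.

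**2. Where the 5 mm matters.** The 20% rise is less than 5 mm when 0.20 × N < 5, that is N < 25 mm.

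| Nadir (mm) | PD from, Table 6 (1.20 × N) | PD from, text (larger of 1.20 × N and N + 5) |
|---|---|---|
| 10 | 12 mm | 15 mm (+50%) |
| 20 | 24 mm | 25 mm (+25%) |
| 25 | 30 mm | 30 mm (+20%) |

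So 20 to 24 mm (+20%, +4 mm) and 10 to 12 mm (+20%, +2 mm) are SD by the text and PD by Table 6, while 25 to 30 mm is PD by both. Given the entry criterion, sums below 25 mm can occur at baseline, and responders can shrink into that range.

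**3. PR and PD together.** In Table 6 both rows can apply when 1.20 × N ≤ 0.70 × B, that is N ≤ 0.583 × B. Example: 100 to 40 to 60 mm is −40% from baseline and +50% (+20 mm) from nadir. Table 6 gives PR and PD. So does the text, because it excludes only CR from PR. For nadirs below 25 mm the text's overlap starts slightly later, at N + 5 ≤ 0.70 × B. For example, 50 to 20 to 24 mm is PR alone by the text but PR and PD by Table 6.

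**4. Effect of the negation rule.** Appendix 1 cancels an irRECIST PD for PFS if the next scan, at least 4 weeks later, is SD, PR or CR. This removes transient calls but not a persistent small rise: 20 to 24 to 24 mm is PD twice under Table 6 and never under the text. The rule also relies on a clear ranking. In 100 to 40 to 60 to 65 mm, the last scan is +62.5% from nadir (65/40) and −35% from baseline. If it were read as PR, it would cancel the progression.

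**The case against.** The best defence is that the prose is the definition and Table 6 only a summary. The footnote to Table 4 and the sentence before Table 5 both make RECIST v1.1 the default where irRECIST is silent, and RECIST v1.1 carries the 5 mm. On missing lesions, Table 6 shows the usual case, as Table 1 does for RECIST v1.1. This has weight but does not settle the matter. Table 6 is titled as definitions, and Tables 4 and 5 print the 5 mm only on the RECIST v1.1 side, which a reader may fairly take as a stated difference.

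Several stronger readings are tempting and are not supported:

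- *The PR/PD overlap is a conflict between table and text.* It is not: both share it, and so does the RECIST v1.1 wording in Appendix 1, 2.1. Section 7.1 (PFS and DoR end at first progression) and Appendix 1, 2.8 (progression measured from the smallest sum) imply that progression governs. What is missing is an explicit statement.
- *Table 6 allows CR with a new non-measurable lesion.* The text settles this: such lesions "cannot be included in the tumor response evaluation, but can be used for CR exclusion", and Table 4 agrees. Only CR versus PR would move.
- *The note on new lesions under Partial Response is a rival PD definition.* It states a necessary condition only.
- *Table 6 produces a substantial rate of false progressions.* Any rate needs a reading error that the documents do not give, and must allow for the negation rule.
- *ORR and DCR shift as well.* Table 4 lets best response follow any number of PD assessments, so one disputed scan does not by itself decide them.

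**Conclusion.** The point holds in a limited form. Table 6 contradicts the irRECIST text on the 5 mm minimum, where it matters only for nadir sums below 25 mm, and on incomplete assessments that already meet PD. In addition, PD's precedence over PR is left implicit in both places. Individual irRECIST PFS and DoR classifications can change, softened by the negation rule. The documents give no tumour-size distribution, so the number of patients affected cannot be derived.

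A reader might infer that the trial's main result is at risk. It is not: the primary 6-month PFR is by RECIST v1.1 (Synopsis, Study Design; Section 2), and the RECIST v1.1 definition contains the 5 mm. irRECIST assessment is by the investigator only (Section 7.2.1). This should be corrected because a progression threshold ought to have one value, not because it overturns the design.

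**What to change.** In Appendix 1:

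1. Table 6, PD row: at least +20% and at least 5 mm above nadir SLD.
2. Table 6, incomplete-assessment row: NE unless the lesions measured already meet PD.
3. Table 4, irRECIST progression cell: add the 5 mm so that it agrees.
4. Both the Response Criteria text and Table 6: state that PD takes precedence over PR. Amending the table alone would leave the overlap in the text.

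Two other places must be reconciled at the same time. Section 6.6.1 refers to irRECIST progression when deciding on treatment after progression, so it must point to one definition; what that treatment rule should be is not addressed here. The later comparison with conventional RECIST (Table 7) uses the same name, irRECIST, for a different PD definition based on enhancing lesions only and without the 5 mm. Unless that is resolved, irRECIST progression stays ambiguous even after Table 6 is corrected.

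The cost is appendix wording and one derivation rule. No new data, scans or patients are needed.
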